AMG	Medicinal Products Act (Arzneimittelgesetz)
AR	Adverse Reaction
BASG	Federal Office for Safety in Health Care (Bundesamt für Sicherheit im Gesundheitswesen)
CRA	Clinical Research Associate
CRF	Case Report Form
CTCAE	Common Terminology Criteria for Adverse Events
DSMB	Data Safety Monitoring Board
eCRF	Electronic Case Report Form
FPFV	First patient first visit
GCP	Good Clinical Practice
GZGG	Hallux Metatarsophalangeal Joint (Großzehengrundgelenk)
i. v.	intravenous
ICH	International Conference on Harmonization
ISF	Investigator Site File
KKS	Coordination Center for Clinical Studies (Koordinierungszentrum für Klinische Studien)
LPLV	Last patient last visit
NA	not applicable
ND	not done
p. o.	per os
ROM	Range of motion
SAE	Serious Adverse Event
SAR	Serious Adverse Reaction
SAS	Statistical Analysis System
SDV	Source Data Verification
SOP	Standard Operating Procedure
SPSS	Statistical Package for the Social Sciences
SUSAR	Suspected Unexpected Serious Adverse Reaction
TMF	Trial Master File
UAR	Unexpected Adverse Reaction
VRS	Verbal Rating Scale
VPRS	Verbal Pain Rating Scale

Individuals/Institutions involved

Sponsor: Medical University of Innsbruck, as representative: Univ. [name]. [name], [name]

Study coordination: PD [name]; University Hospital for Orthopaedics of Innsbruck, [name]; [contact]; [contact]; E-Mail: [contact]

Data management: [name]; University Hospital for Orthopaedics of Innsbruck, [name]; [contact]; [contact]; E-Mail: [contact]

Monitoring: [name]; [name]

Biometrics: Mag. [name]; Department for Experimental Orthopaedics, [name]; [contact]; [contact]; E-Mail: [contact]

Synopsis

Sponsor	Medical University of Innsbruck
Title	Continuous wound infiltration after hallux valgus surgery
Abbreviated Designation	CWI-HVS
Target Population	Patients who undergo hallux valgus surgery.
Study Design	Prospective, Randomized, Double-blind, Placebo-controlled Trial
Study Aims	
Primary Study Aim : Proof that there is a significant difference in pain between continuous wound infiltration and placebo during the first 48 postoperative hours.
 
Secondary Study Aim: Proof that there is a significant difference in patient satisfaction and in the amount of rescue medication needed between continuous wound infiltration and placebo during the first 48 postoperative hours.

Study endpoints (dependent variables)	
Primary endpoint Average and maximum VPRS (verbal pain rating score) for pain during the first 48 postoperative hours.
 
Secondary endpoints (1) Endpoints related to safety during treatment period: occurrence of AEs, ARs and UARs. (2) Endpoints related to effectiveness: patient satisfaction (VRS), clinical outcome (AOOFAS forefoot score, ROM GZGG after 6 weeks), pain (VPRS) after 1, 2 and 6 weeks, need for rescue pain medication

Number of Patients	50
Schedule	
Study-related Recruitment time: 1 Year Planned Start (FPFV): 01-03-2014 Planned Study Completion (LPLV): 06/2017
 
Patient-related Duration of treatment: 6 weeks

Inclusion Criteria	
 Male and female patients over the age of 18 years Written consent of the patient after information Patients undergoing a distal metatarsal osteotomy (only Chevron or Scarf) and lateral release of the adductor hallucis muscle with/without concomitant osteotomy of the proximal phalanx of the great toe (Akin) for idiopathic hallux valgus deformity.

Exclusion Criteria	
 • A history of hypersensitivity / contraindication to one of the drugs administered, their ingredients or to drugs with a similar chemical structure. • Other methods of hallux valgus surgery / additional surgeries than those mentioned. • Neurological disorder that affects the sensorimotor function. • Surgery with general anaesthesia. • Surgery on the same leg within the last month. • Existing pregnancy.
Course of the Study	
See study protocol:
 
Visit 1 (day 0): admission and consent to study
 
Visit 2 (day 1-3): surgery (day 1) and stay in hospital
 
Visit 3 (day 7 ± 3): 1st outpatient follow-up
 
Visit 4 (day 14 ± 3): 2nd outpatient follow-up
 
Visit 5 (final visit, day 42 ± 7): 3rd outpatient follow-up

Study-related Procedures and Laboratory Examinations	AOFAS forefoot score (1x presurgical and 1x postsurgical), 1x presurgical pregnancy test
Trial Medication	
Agent: ropivacaine 0.2 %
 
Trade name: Ropinaest®2 mg/ml
 
Manufacturer: Gebro Pharma GmbH, Fieberbrunn, Austria

1.1 Study background

Hallux valgus surgeries are orthopaedic surgeries which are performed on a frequent basis and which lead to significant pain, in particular within the first 24 postoperative hours. Continuous wound infiltration by means of local anaesthetic in the framework of multi-modal pain therapy has already been tested in many other surgeries (abdominal surgery, shoulder surgeries, hip and knee joint endoprosthetics).

1.2 Need for the study to be conducted

In particular within the first 24 postoperative hours, hallux valgus surgeries lead to significant pain even though NSAR and opiates are routinely administered. In order to further improve pain therapy, a multi-modal pain therapy is necessary. So far, the use of continuous wound infiltration following hallux valgus surgery has not been investigated. In order to prove the effectiveness of continuous wound infiltration by means of a local anaesthetic, the comparison with a placebo group is necessary. The routine use of continuous wound infiltration could further improve postsurgical pain therapy following hallux valgus, and could thus contribute to a higher patient satisfaction.

1.3 Risk/Benefit assessment

So far, other studies have reported no increased rate in local or systemic complications by insertion of a pain catheter and by usage of continuous wound infiltration, even when higher doses of the local anaesthetic were administered. The advantage of the method lies in particular in the local action mechanism with only small effects on the rest of the body.

Ropivacaine is, due to its favourable side effect profile, the local anaesthetic used most frequently for this indication. Possible side effects of ropivacaine include decrease/increase in blood pressure as well as in the heart rate, vertigo, headaches, nausea including vomiting, tingling and fever. Sudden life-threatening allergic reactions are rare and concern 1 to 10 treated persons out of 10000. Further serious side effects, which could be caused by an overdosage of Naropin, include problems when speaking, muscle twitching, trembling, convulsions and loss of consciousness.

Applying the study therapy could result in a reduced need for systemically effective analgesics and in less postsurgical pain. The head of the study deems the risk/benefit ratio favourable.

The study visits will be carried out in the course of the routine clinical follow-up examinations after 1, 2 and 6 weeks. This does not result in any additional risk or any additional stress for the patients.

2 Study aims

2.1 Primary study aim

The aim of this study is to document the effect of a postsurgical continuous wound infiltration in comparison with standard treatment. The average and maximum postsurgical pain during the first 48 postoperative hours was chosen as primary endpoint, which shall be recorded by means of VRS (verbal rating scale) for pain:

The null hypothesis is as follows: during the first 48 hours, there is no significant difference in postsurgical pain between continuous wound infiltration with Ropinaest® and placebo.

The alternative hypothesis is as follows: during the first 48 hours, there is a significant difference in postsurgical pain between continuous wound infiltration with Ropinaest® and placebo.

The significance level is chosen with $p < 0.05$.

2.2 Secondary study aims

The need for rescue pain medication, the patients' satisfaction with surgery and pain therapy (collected by means of VRS) and the clinical outcome (collected by means of AOFAS forefoot score) were defined as parameters of secondary objective. Furthermore, the occurrence of UAEs and AEs is collected. These shall be collected in a purely descriptive manner.

3 Description of the study

3.1 Study design

This is a monocentric, randomized, double-blind, placebo-controlled study.

3.2 Primary endpoint of the study

The average and maximum postsurgical pain during the first 48 postoperative hours was chosen as primary endpoint which shall be recorded by means of VPRS (verbal pain rating scale) for pain.

3.3 Secondary endpoint of the study

The need for rescue pain medication, the patients' satisfaction with surgery and pain therapy (collected by means of VRS) and the clinical outcome (collected by means of AOFAS forefoot score) were defined as parameters of secondary objective. Furthermore, the occurrence of UAEs and AEs as well as the need for rescue pain medication is collected.

3.4 Number of patients

The study includes a total of 50 patients, 25 of which are in the verum group and 25 of which are in the placebo group.

3.5 Schedule

The time needed for recruitment is estimated to be 1 year. Planned start (FPFV) is on 01-03-2014, planned study completion (LPLV) is on 31-06-2017. The duration of treatment including follow-up examination is 6 weeks.

4 Patient population

4.1 Inclusion criteria

- Male and female patients over the age of 18 years
- Written consent of the patient after information
- Patients undergoing a distal metatarsal osteotomy (only Chevron, Scarf) and lateral release of the adductor hallucis muscle with/without concomitant osteotomy of the proximal phalanx of the great toe (Akin) for idiopathic hallux valgus deformity.

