4.2 Exclusion criteria

- A history of hypersensitivity / contraindication to one of the drugs administered or to their ingredients or to drugs with a similar chemical structure.
- Other methods of hallux valgus surgery and additional surgeries of the little toes other than those mentioned.
- Neurological disorder that affects the sensory-motor function.
- Refusing to participate in the study or refusal of consent to study.
- Existing pregnancy.
- Surgery on the same leg within the last month.
- Surgeries with general anaesthesia.

5 Trial medication

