5.4 Randomization

Randomization takes place in 2 groups as balanced randomization by means of a computer-generated random number sequence. This random number sequence is generated with the help of the website www.random.org (numbers, random sequence generator). The first 25 results are assigned to the verum group, the other 25 results are assigned to the placebo group. Upon admission to the study, the patients receive at random one of these numbers which are contained in sealed envelopes on which the numbers 1 to 50 are written. The randomization envelope is opened by an independent member of the nursing staff – who is not involved in the further treatment of the patient – several minutes prior to the start of surgery. Such member will fill a 50 ml perfusor syringe with either ropivacaine 0.2 % or physiological saline solution. The patients, surgeons as well as the care-taking nursing staff are blinded as regards the content. The deciphering list will only be opened after conclusion of the last follow-up examination.

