6.1 Visit 1 (baseline, day 0)

Prior to admission to the clinical trial, every patient must be informed in detail on the study. Information takes place in person by the treating doctor and in writing by means of the patient information. Only after all questions of the patient have been answered, he/she will be asked to sign two copies of the declaration of consent and to personally date it. Following this, the patient receives a copy of the patient information/declaration of consent; the second copy is kept in the investigator site file.

Upon visit 1, demographic data (age, sex, weight, size, BMI, side) is recorded. Furthermore, physical examination is carried out, including examination of the range of motion (ROM) of the hallux metatarsophalangeal joint (GZGG) as well as assessment of AOFAS forefoot score by means of the "AOFAS Hallux Metatarsophalangeal-Interphalangeal Scale" questionnaire and the average and maximum VPRS. Women of childbearing age undergo laboratory testing to exclude pregnancy. After final examination of the inclusion and exclusion criteria, the patient is admitted to the study, including his admission to one of the two treatment groups according to randomization as explained above.

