11.1 Sample size planning

Statistical planning and analysis takes places under the direction of Mag. [name] of the Institute for experimental orthopaedics.

By using the software G*Power (Franz Faul, University of Kiel, Germany), an a priori sample size analysis is carried out. The following parameters shall be assumed for the calculation of the optimal sample size:

- Primary target variable: average VRS (verbal rating scale; 0-10) for pain
- Clinically-relevant difference: 1
- Number of groups: 2 (same group size)
- Statistical methods:
 - Test family: t-test
 - Statistical test: means; difference between two independent means (groups)
 - Type of power analysis: a priori
- Formulation of hypothesis: two pages
- Effect size: Cohen's $d = 1$ (large effect size)
 - assumed mean difference: 1
 - assumed standard deviation: 1
- Type 1 error: 5 %
- Type 2 error: 20%
- Test power: 80%

- Group size: N1=N2
- Drop-out rate: approx. 10 %

An a priori sample size analysis using the parameters mentioned above, results in a targeted minimal power of 0.80 and with a Cohen's d of 1 (reveals large effects) results in a number of 34 people necessary (17 per group). Considering that the drop-out rate is expected to be at 10 %, the optimal sampling size is 40 feet (20 per group). By means of the sampling size used by us, it should be possible to reveal effects of large size with sufficient power.

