11.2 Randomization

Randomization takes place in 2 groups as balanced randomization by means of a computer-generated random number sequence. This random number sequence is generated with the help of the website www.random.org (numbers, random sequence generator). The first 20 results of this list are assigned to the verum group, the other 20 results are assigned to the placebo group. Upon admission to the study, the patients receive at random one of these numbers which are contained in sealed envelopes on which the numbers 1 to 40 [sic] are written. The randomization envelope is opened by an independent member of the nursing staff – who is not involved in the further treatment of the patient – several minutes prior to the start of surgery. Such member will fill a 50 ml perfusor syringe with either ropivacaine 0.2 % or physiological saline solution. The patients, surgeons as well as the care-taking nursing staff are blinded as regards the content. The deciphering list will only be opened after conclusion of the last follow-up examination.

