11.3.3 Data analysis

Confirmatory data analysis

The primary dependent variables (average and maximum VRS for pain during the first 48 postoperative hours) shall be analysed in a confirmatory way for two independent samples using a t-test. This shall be done by means of the current version of the software SPSS Statistics (company IBM, Armonk, New York, USA).

Exploratory data analysis

All secondary dependent variables – patient satisfaction (VRS), clinical outcome (AOFAS forefoot score, ROM GZGG after 6 weeks), maximum and average pain (VPRS) after 1, 2 and 6 weeks – shall be analysed in a purely descriptive way by means of using the current version of the software SPSS Statistics (company IBM, Armonk, New York, USA).

12 Reporting

Minutes of the meetings of the different committees are drawn up in order to document the process and development of the study.

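### A cheap improvement, not an error: record the type of osteotomy and adjust the primary pain analysis for it, since Chevron and Scarf, with or without Akin, are pooled in a plain t-test

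*Combined protocol and SAP*

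**What the plan says.** Section 4.1 makes eligible a "distal metatarsal osteotomy (only Chevron, Scarf) and lateral release of the adductor hallucis muscle with/without concomitant osteotomy of the proximal phalanx". That gives four combinations: Chevron or Scarf, each with or without Akin. Section 4.2 narrows the field by excluding "Other methods of hallux valgus surgery and additional surgeries of the little toes other than those mentioned".

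Section 5.4 describes one allocation list and names no strata: "Randomization takes place in 2 groups as balanced randomization by means of a computer-generated random number sequence". Only the arm totals are fixed: "The first 25 results are assigned to the verum group, the other 25 results are assigned to the placebo group". Section 11.2 describes the same scheme with 20 per arm ("The first 20 results of this list are assigned to the verum group"). The conflict between 50 and 40 patients is a separate matter, so both totals are carried through below.

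Under section 11.3.3, average and maximum pain over the first 48 hours "shall be analysed in a confirmatory way for two independent samples using a t-test", with no covariate. The sample size in section 11.1 uses a mean difference of 1 and "assumed standard deviation: 1", without a source and without saying whether that SD holds within or across operations. At visit 1 (section 6.1), "demographic data (age, sex, weight, size, BMI, side) is recorded", along with joint motion, AOFAS score and pain. The type of operation is not listed.

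**The concern.** The primary endpoint is pain after an operation whose bony extent varies between patients. The extent of surgery is therefore a natural candidate to predict the outcome, and preoperative pain does not describe it. Section 4.2 already treats the kind of surgery as worth controlling, but the variation that remains enters neither the randomization nor the analysis.

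If pain differs between the operations, the unadjusted t-test carries that difference in its error term, and power is lower than an adjusted analysis of the same patients would give. If the operation is not recorded in the CRF, the covariate may be missing from the trial database. If the model is not prespecified, any adjustment made after seeing an unequal mix would be post hoc.

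**Working it through.** **Inputs.** From section 11.1: difference 1, SD 1, type 1 error 5% (taken as two-sided), power 80%, dropout about 10%. From sections 3.4 and 5.4: 25 per arm. From sections 11.1 and 11.2: 20 per arm. Assumed, because the documents give no figure: the mean pain difference d between Chevron and Scarf (range 0 to 1 point) and the share p having one of them (0.5, with 0.3 as a check).

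**The plan's own figure.** Noncentral t, n per arm, 2n − 2 degrees of freedom, noncentrality (1/SD)·√(n/2). With SD 1, n = 17 gives power 0.807 and n = 16 gives 0.781, so the stated 34 patients reproduce. Dividing 34 by 0.9 gives 38, which the plan takes up to 40.

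**Evaluable numbers.** 40 × 0.9 = 36, or 18 per arm. 50 × 0.9 = 45, taken as 22 per arm.

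**Reading A: SD 1 is the SD within an operation.** The t-test then works with the pooled SD, √(1 + p(1 − p)d²). With p = 0.5:
- d = 0.5: √(1 + 0.25 × 0.25) = 1.031
- d = 1: √(1 + 0.25 × 1) = 1.118

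The adjusted model keeps a residual SD of 1, has N − 3 degrees of freedom, and pays an average variance factor of (N − 3)/(N − 4) for chance imbalance, where N = 2n.

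| Evaluable per arm | t-test, d = 0 | d = 0.5 | d = 1 | Adjusted, any d |
|---|---|---|---|---|
| 18 (from 40) | 0.830 | 0.807 | 0.741 | 0.818 |
| 22 (from 50) | 0.900 | 0.882 | 0.826 | 0.892 |

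**Reading B: SD 1 is the total SD of the pooled population.** The t-test has its planned power whatever d is. The adjusted residual SD is √(1 − p(1 − p)d²), which with p = 0.5 is 0.968 at d = 0.5 and 0.866 at d = 1. With 20 per arm, all evaluable, power rises from 0.869 to 0.880 (d = 0.5) or 0.939 (d = 1).

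**Break-even.** Adjustment pays once the operation explains more than 1/(N − 3) of the outcome variance. For 36 to 50 analysed patients this corresponds to d of about 0.30 to 0.35 points with a 50:50 mix, or 0.32 to 0.39 with 70:30.

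**Imbalance.** With 25 per arm, 25 of 50 patients having Scarf and d = 1, the shift in the treatment estimate due to unequal mix has an SD of 0.143 (hypergeometric), a variance of 0.02. The within-operation part is 2 × 1/25 = 0.08. Together they make 0.10, which is the t-test's own variance, 2 × 1.25/25 = 0.10 (standard error 0.32). The imbalance is thus already inside the standard error.

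**Type I error.** In 40,000 simulated trials per setting, with 20 and 25 per arm and d = 1 and 2, the unadjusted test rejected a true null in 0.049 to 0.051 of runs.

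**The case against.** The strongest reply is that the premise is not shown. No section reports pain by operation or the expected mix, and every power loss above depends on an assumed d. The plainest reading of section 11.1 is also that SD 1 describes the patients to be enrolled, operations mixed; then pooling costs nothing against the plan. Heterogeneity is limited besides: one centre, two osteotomies, lateral release in everyone, other procedures and general anaesthesia excluded, and a common analgesic regimen with pain-triggered rescue that may narrow recorded differences. All of this stands, and it is why the point is an improvement and not a defect.

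Two further objections shape the fix. First, a reader might infer from the eligibility rule that the specific osteotomy is settled at visit 1. It does not follow: section 4.1 accepts either osteotomy, with or without Akin, so eligibility can be confirmed without knowing which. Second, four combinations are pooled, but the calculation covers only Chevron against Scarf. Adding Akin to the main model would spend a second degree of freedom in 36 to 50 patients with no documentary evidence that it predicts pain, so it belongs in a sensitivity model.

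What the reply does not remove is the asymmetry. If the operation is irrelevant, adjusting costs about 0.01 in power. If operations differ by more than about a third of a point, adjusting gains under either reading of the SD.

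**Conclusion.** An optional gain in efficiency at low cost. At d = 1 under reading A, adjustment recovers about 0.08 in power with 18 per arm (0.74 to 0.82) or about 0.07 with 22 per arm (0.83 to 0.89). At d = 0.5 the gain is about 0.01 in both cases. Under reading B the planned power is met without adjustment and improved with it. These figures rest on the assumed d, the 50:50 mix, 10% dropout where stated, and planned and performed operations being the same.

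Three stronger conclusions are tempting and are not supported:
- That the primary test is invalid or biased. Randomization keeps its type I error at about 5%.
- That the trial is underpowered because of pooling. That needs SD 1 to be a within-operation figure and d to be sizeable: with 22 evaluable per arm, power falls below 0.80 only at d of about 1.2, more than the plan's whole clinically relevant difference. With 18 per arm the threshold is lower, but the documents establish neither condition.
- That chance imbalance could mimic or hide an effect as a further harm on top of the noise. It is the same variance, already counted in the standard error.

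**What to change.** Before unblinding:
1. Add two items to the CRF: osteotomy type (Chevron or Scarf) and Akin (yes or no). Record the operation as planned before the randomization envelope is opened, so that allocation cannot influence the factor.
2. Amend section 11.3.3 so that average and maximum VPRS are each analysed by a linear model with arm and osteotomy type as factors, reporting the arm coefficient with its 95% confidence interval as the confirmatory result.
3. Keep the plain t-test as a sensitivity analysis, and add Akin as a second factor in a further sensitivity model.
4. State in section 11.1 whether the SD of 1 is meant to cover the pooled population.

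The cost is a few lines of SAP text, two CRF items and one degree of freedom. If the operation is unrelated to pain, power falls from 0.830 to 0.818 with 18 per arm, or from 0.900 to 0.892 with 22 per arm. Sample size, randomization and patient care are unchanged.
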